#### **Visualizing Glomerular Injury: A New Frontier with Ultrasound Localization Microscopy**

Ultrasound Localization Microscopy (ULM) is an **advanced and highly sensitive ultrasound imaging technique** that allows visualisation of the microvasculature and quantification of dynamic blood flow changes within the vascular architecture with unprecedented resolution. Tiny air bubbles (microbubbles) are administered intravenously as contrast agents, which can then be localised and tracked within each image of the ultrasound acquisition [15]. Accumulation of all these tracks on a 2D grid produces a microvascular map of the organ with a resolution beyond the diffraction limit of ultrasound waves. Unlike other types of contrast agents, the microbubbles are subsequently metabolised independently of kidney and liver function and will simply be washed out by respiration [16]. ULM has been used in several human organs [17-19]. Two studies have already been performed at the Department of Pediatrics and Adolescent Medicine (University Hospital Erlangen) using ULM to visualise the microvascular architecture in the neonatal brain and to quantify dynamic perfusion changes [18, 20]. Moreover, a study with ULM in kidney transplants has been successfully conducted, proving the feasibility of the method in patients with renal impairment. More recently, the glomerulus, the smallest functional unit of the kidney, has been visualised in the human body

with high resolution [21]. Glomerular injury is closely linked to vascular damage in the kidneys, as endothelial dysfunction and microvascular injury impair glomerular filtration and contribute to progressive renal dysfunction.

The aim of this study is to facilitate the early visualization of glomerular damage representing a vascular component of chemotherapy induced nephrotoxicity by ULM. This approach could contribute to the timely detection of functional kidney impairment - even earlier than potential albuminuria - and thus help to adapt follow-up structures and measures or even revise treatment protocols. In the frame of this pilot study, we focus on individuals with a history of ALL, as they represent by far the largest and most extensively studied subgroup of patients in pediatric oncology. Therefore, we expect a sufficient number of patients in this monocentric approach.

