### Graphical design of study flow

**Figure 1: Course of Study**

**STUDY POPULATION / IN- AND EXCLUSION CRITERIA**

Early therapeutic effects	Late therapeutic effects
Planned number of patients	
N = 10 ALL (recently diagnosed ALL)	N = 20 ALL (completed oncological treatment)
Planned number of examinations for each participant	
2 (before first CPM according to therapy protocol and after completion of intensive therapy)	1
Inclusion criteria	

 
- Diagnosed acute lymphatic leukemia
 
- Treatment day < 50 according to therapy protocol / no administration of CPM before first examination
 
- From 3 years to < 18 years
 
	
 
- Diagnosed acute lymphatic leukemia
 
- Completed oncological treatment
 
- From 3 years to < 18 years
 

Exclusion criteria	

 
- Known allergic disposition to SonoVue / other contrast agents
 
- Tattoo in the area of the examination field
 
- Pregnancy
 
- Breastfeeding mothers
 
- Contraindication for the use of Sonovue
 
- Critical condition
 
	
 
- Known clinically evident renal impairment
 
- Known allergic disposition to SonoVue / other contrast agents
 
- Tattoo in the area of the examination field
 
- Pregnancy
 
- Breastfeeding mothers
 
- Contraindication for the use of Sonovue
 
- Critical condition
 

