**Number of patients**

As this is a pilot study, it is not possible to calculate the exact number of patients. It is planned to include 30 patients (in total 40 examinations). The planned sample size of 30 participants (10 during therapy and 20 in follow-up) was determined based on the annual incidence of ALL at our center, which is approximately 15 cases per year. Recruitment within the intended timeframe of 12–18 months is therefore considered feasible. In addition, the study has a pilot character, aiming to provide the first data set for estimating effect sizes and to serve as a foundation for the design of larger subsequent studies. 10 patients who will undergo an ULM examination of the kidney before the start of chemotherapy, latest before therapy day 50 before the first application of high-dose methotrexate or cyclophosphamide (Timepoint 1). After completion of intensive therapy (after administration of cyclophosphamide and high-dose methotrexate), they will receive a follow-up ULM

Contents are confidential. No disclosure to third parties.

examination (Timepoint 2) approx. 6-9 months after the first ULM examination. In addition, 20 different patients who have completed treatment for ALL and are seen during aftercare will be included in the study.

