### **Calculation of case numbers**

As this is a pilot study and no information is yet available on the expected differences between the different groups, no calculation of the number of cases has been made. The number of cases given is an estimate.

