### **Statistics**

The data is given as a mean value with standard deviation. Correlations are indicated with the non-parametric Spearman correlation coefficient (Rs). Differences in the mean values are analysed statically using a non-parametric T-test (Mann-Whitney test) or ANOVA. In all analyses, an error level of <0.05 is considered statically significant.

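### The pilot is meant to supply effect sizes for later studies, but the outputs named under Statistics do not give the paired effect size, or its uncertainty, for the 10 patients scanned twice

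*Protocol*

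**What the plan says.** Under Number of patients, the protocol plans 30 patients and 40 examinations. Ten recently diagnosed patients are scanned twice, about 6 to 9 months apart, and 20 different patients who have finished treatment are scanned once. The number rests on local incidence and feasible recruitment. The pilot is further described as "aiming to provide the first data set for estimating effect sizes and to serve as a foundation for the design of larger subsequent studies".

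Calculation of case numbers gives a second reason for having no calculation: "no information is yet available on the expected differences between the different groups, no calculation of the number of cases has been made".

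The Statistics section fixes the output. For description it says "The data is given as a mean value with standard deviation". For comparison it says "Differences in the mean values are analysed statically using a non-parametric T-test (Mann-Whitney test) or ANOVA". Correlations are Spearman coefficients, and the Secondary objectives show that these relate ULM values to laboratory and sonographic values, not the first scan to the second. On inference it adds only that "In all analyses, an error level of <0.05 is considered statically significant". It names no change score, paired analysis, effect-size estimate or interval.

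**The concern.** The stated aim is estimation, while the stated outputs are per-group summaries and significance tests. The mismatch matters most for the 10 patients with two scans, who hold all the longitudinal information in the study. A paired effect size is the mean within-patient change divided by, or read against, the SD of that change. Means and SDs given visit by visit do not contain that SD, and Mann-Whitney treats the two visits as if they came from different patients.

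If the section is followed as it stands, 20 contrast examinations in 10 children could be reported without the one quantity that a longitudinal follow-on study would need, and without a measure of how well it is known.

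**Working it through.** **The plan's own figures.** 10 + 20 = 30 patients, and 10 × 2 + 20 × 1 = 40 examinations. Both agree with the protocol. There is no power calculation to reproduce.

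**Inputs.** From the protocol: 10 pairs, 20 single-visit patients, significance level 0.05. Not in the protocol, and assumed here: a two-sided level, equal SDs at the two visits, within-patient correlation r shown over a range, approximate normality, no dropout, and, for illustration only, 80% power for a later study to detect a difference of 0.5 SD.

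**Step 1: what per-visit SDs leave open.** With a common SD, SD of change = SD × √(2(1 − r)).
- r = 0.2: √1.6 = 1.26 SD
- r = 0.8: √0.4 = 0.63 SD

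The required number of pairs is proportional to the square of this SD, so the ratio is 1.6 / 0.4 = 4.

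**Step 2: the same in patients.** n = (SD of change)² × (1.960 + 0.842)² / 0.5², in units of SD, rounded up.

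| Assumed r | SD of change | Pairs (normal approximation) | Pairs (noncentral t) |
|---|---|---|---|
| 0 | 1.41 | 63 | 65 |
| 0.2 | 1.26 | 51 | 53 |
| 0.5 | 1.00 | 32 | 34 |
| 0.8 | 0.63 | 13 | 15 |
| 0.9 | 0.45 | 7 | 9 |

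Reporting the SD of change would replace this range with an estimate.

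**Step 3: what can still be derived from mean, SD and n.** An unpaired study can be sized: 63 per arm for 0.5 SD and 25 per arm for 0.8 SD (two-sided 0.05, 80% power). Intervals for single group means, for group SDs and for the difference between two independent groups also follow from mean, SD and n.

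**Step 4: the precision the pilot can offer.** The half-width of a 95% CI for a mean is t(0.975, n − 1) / √n.
- 10 pairs: 2.262 / 3.162 = 0.72 SD of change
- 20 patients: 2.093 / 4.472 = 0.47 SD
- 10 versus 20 patients, common SD: 2.048 × √(1/10 + 1/20) = 0.79 SD

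None of these needs an expected difference, so they could have been stated despite the reason given under Calculation of case numbers.

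**Step 5: how well 10 pairs fix the SD of change.** The 95% limits are √(9/χ²), or 0.69 to 1.83 times the observed SD. Squared, that is 0.47 to 3.33 times on a later sample size.

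**The case against.** The strongest reply is that this is detail for an analysis plan. Only the protocol is at hand, and a separate plan may add change scores and intervals. The protocol promises a data set, and patient-level values will be kept, so the SD of change can be computed at any time. The sentence on means and SDs does not say visit by visit and does not rule out change scores. ANOVA could be meant in its repeated-measures form, which would keep the pairing. Most of this stands, and it limits the point. It does not remove it: the Statistics section does commit to outputs, and its only named two-group test is for independent samples. What it commits to does not match the aim stated under Number of patients.

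A reader might also infer more than the documents support:

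- **That the next study could not be sized at all.** An unpaired study can be sized from mean and SD (Step 3), and a paired one could be sized cautiously at r = 0.
- **That the report would carry no information on uncertainty.** Several intervals follow from mean, SD and n. The paired change is the exception, and intervals for the Spearman coefficients are simply not planned.
- **That a later study would more often than not be underpowered.** Sized for 80% power on the raw SD from 10 pairs, it would have a 56% chance of true power below 80% and a 37% chance of power below 70%. That assumes a later team takes the point value with no allowance, which the protocol nowhere says. The figures describe any SD from 10 observations, and printing an interval does not change them.
- **That variability was already to hand.** The background says that "a study with ULM in kidney transplants has been successfully conducted", but reports only feasibility, with no SDs or repeat scans.
- **That the feasibility argument is wrong.** Recruitment capacity is an acceptable basis for a pilot. Number of patients cites pilot character, incidence and recruitment; only Calculation of case numbers cites unknown differences.

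**Conclusion.** The point holds in a limited form. For the 10 patients scanned twice, the named outputs do not deliver the paired effect size or its uncertainty, although estimating effect sizes is a stated purpose of the pilot. What is left open is a four-fold range in a later paired sample size for r between 0.2 and 0.8. The correlations and the equal SDs are assumptions, because the protocol gives neither.

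This does not threaten the conduct of the study or its unpaired comparison, and no information is lost for good. It should be corrected because the present wording sets aside the pairing that the design pays for. Even when corrected, the paired estimate will be rough: about ±0.72 SD of change for the mean, assuming approximate normality and all 10 pairs complete.

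**What to change.** **Statistics.** For each primary perfusion parameter in the 10 pairs, report the mean within-patient change (Timepoint 2 minus Timepoint 1), the SD of that change and a 95% CI for the mean change. State that these data are analysed as paired, and keep Mann-Whitney for the comparison of different patients. Give the between-cohort difference and each Spearman coefficient with a 95% CI.

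**Number of patients and Calculation of case numbers.** Keep the feasibility justification. Add the expected precision: a 95% CI half-width of about 0.72 SD of change with 10 pairs and about 0.47 SD with 20 patients, under approximate normality. This protocol need not commit to how later studies will be sized.

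**Cost.** A few sentences and a few more table columns, with no extra patients or scans. The stated precision will look modest.

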## **OBJECTIVES**

### **Hypotheses**

- ULM can be used to visualise and quantify the microvascular perfusion dynamics in the kidney and differs depending on the organ function
- Treatment of acute lymphoblastic leukaemia leads to (often subclinical) acute and chronic impairment of renal function also through vascular injury which can be visualized by ULM.

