### **Primary objectives**

- ULM: Visualisation of microvascular architecture and Quantification of microvascular perfusion dynamics in the kidney before, during, and after treatment of acute lymphoblastic leukaemia

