### **Study arms: interventional/control**

Patients fulfilling the inclusion criteria will receive ULM of one kidney. Patients with recently diagnosed ALL will receive ULM at two timepoints whereas participants in the oncological follow up after treatment for ALL will be examined at a single visit.

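### A chronic treatment effect can be read only from an unnamed survivors-versus-early-cohort contrast, and the tests listed for it carry no age term

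*Protocol*

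**What the plan says.** The second hypothesis (Protocol, Hypotheses) is causal: "Treatment of acute lymphoblastic leukaemia leads to (often subclinical) acute and chronic impairment of renal function", visible by ULM. The primary objective is to visualise and quantify "microvascular perfusion dynamics in the kidney before, during, and after treatment of acute lymphoblastic leukaemia".

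Two cohorts supply the data. Ten recently diagnosed patients are scanned twice. The late cohort is separate: "In addition, 20 different patients who have completed treatment for ALL and are seen during aftercare will be included in the study". Under Study arms, "participants in the oncological follow up after treatment for ALL will be examined at a single visit". Both cohorts must be aged 3 to under 18 years. No matching or stratification on age is described, randomisation is ruled out, and no healthy or external reference group is mentioned. Known clinically evident renal impairment is an exclusion for the late cohort only.

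Calculation of case numbers explains the absence of a power calculation by saying that "no information is yet available on the expected differences between the different groups". Statistics then states: "Differences in the mean values are analysed statically using a non-parametric T-test (Mann-Whitney test) or ANOVA". No covariate is mentioned.

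Among the pilot's purposes, Number of patients lists "aiming to provide the first data set for estimating effect sizes and to serve as a foundation for the design of larger subsequent studies".

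**The concern.** A survivor scanned once cannot show a change. Correlations within survivors, which the secondary objectives plan, can show whether ULM tracks renal markers, but not that treatment altered anything. The only other ULM data are the early cohort's two scans. So the chronic part of the hypothesis rests on a comparison between different children, and the Protocol says neither that it will be made nor whether Timepoint 1 or Timepoint 2 is the reference.

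The listed tests compare the cohorts as they come. If survivors are older or younger at scan and the ULM parameter changes with age, part or all of the observed difference is growth rather than treatment. Since the pilot is meant to supply effect sizes for larger studies, that error would pass into their design labelled as a treatment effect.

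**Working it through.** **Plan's own figures.** 10 + 20 = 30 patients; 10 × 2 + 20 × 1 = 40 examinations. Both match Number of patients. The Protocol states no effect size, SD or power, so there is none to reproduce.

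**Inputs.** Cohort sizes of 10 and 20, the 3 to <18 year window and the 0.05 level come from the Protocol; two-sided testing is assumed. The following are also assumptions, not document figures: age SD of 4 years within cohort, correlation r of the ULM parameter with age of 0.3 to 0.7, the age gap between cohorts, and no true treatment effect.

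**Bias.** With y = r × age/4 + √(1 − r²) × noise, the within-cohort SD is 1 and the spurious difference is r × gap/4. For a 2-year gap and r = 0.5 this is 0.5 × 2/4 = 0.25 SD. If r is negative, so is the bias. False-positive rates come from 40,000 simulated data sets per setting, using the exact Mann-Whitney critical value (exact level 4.9%).

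| Realised gap | Spurious difference (SD), r = 0.3 / 0.5 / 0.7 | Mann-Whitney false positives |
|---|---|---|
| None, or r = 0 | 0 | 4.7–5.1% |
| 1 year | 0.08 / 0.13 / 0.18 | 5.4 / 5.8 / 7.1% |
| 2 years | 0.15 / 0.25 / 0.35 | 6.4 / 9.3 / 13.4% |
| 3 years | 0.23 / 0.38 / 0.53 | 8.2 / 14.5 / 24.7% |

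A separate run of 4,000 data sets per setting gave the same biases and similar rates (6.0 / 8.0 / 12.8% at 2 years; 7.4 / 13.2 / 23.2% at 3 years).

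**Effect of the age window.** Survivors may have been diagnosed before age 3, and those who reach 18 are no longer eligible, so the window narrows any gap. Nominal shifts of 2, 3 and 5 years, truncated to 3 to <18 and centred at 10.5, become 1.44, 2.15 and 3.51 years. With the same slope the bias is 0.11–0.25, 0.16–0.38 and 0.26–0.61 SD (for example 3.51 × 0.7/4 = 0.61), with 6–10%, 7–17% and 10–38% false positives.

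**How large the gap could be.** Under assumed diagnosis-age distributions, with survivors scanned 2–5 or 2–10 years after diagnosis:

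- diagnosis age uniform over 0–18 years: gap of 0.3 or 1.3 years;
- gamma with mean 6 years, shape 2: 1.8 or 3.7 years;
- gamma with mean 6 years, shape 3: 2.4 or 4.4 years.

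**Sampling error for comparison.** SE = √(1/10 + 1/20) = 0.387 SD. With 28 degrees of freedom the 95% half-width is 2.048 × 0.387 = 0.79 SD.

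**Consequence for the next study.** Sample size per group is 2 × (1.960 + 0.842)²/d², or 15.70/d² with unrounded quantiles. Assume a true effect of 0.5 SD and a bias of 0.25 SD.

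- Correct effect, d = 0.5: 15.70/0.25 = 62.8, so 63.
- Bias adds, d = 0.75: 15.70/0.5625 = 27.9, so 28. True power at d = 0.5 is then Φ(0.5 × √14 − 1.96) = Φ(−0.09) = 46%.
- Bias subtracts, d = 0.25: 15.70/0.0625 = 251.2, so 252.

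**With an age term.** A linear model on cohort and age at scan gave a bias of about zero and 4.7–5.2% false positives throughout; a rank version gave 4.9–5.8%. If the true age relation flattens at 12 years, the linear term leaves 0.01–0.07 SD, against 0.12–0.75 SD unadjusted.

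**The case against.** The strongest reply is that this belongs in a statistical analysis plan, which may exist and may adjust for age. The Protocol calls the study exploratory, its primary objective can be met descriptively, and it never commits to a survivors-versus-early contrast. The effect sizes it hopes for might be the paired changes in the early cohort or the correlations, neither of which the age gap between cohorts would distort. An ANOVA with unstated factors does not exclude an age term.

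This limits the weight of the point without removing it. The Protocol states its own tests for group differences, without a covariate. Which comparison answers a stated hypothesis, and against which timepoint, is a design matter. The paired change does not inform the late cohort at all.

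Two further objections stand as qualifications. First, every input to the magnitude is assumed, and at a 1-year gap the false-positive rate is 5–7%, close to nominal. Second, chance alone can mis-size the next study: with a true effect of 0.5 SD and no age bias, the estimate misses by 0.25 SD or more with probability 2 × P(Z > 0.25/0.387) = 52%. The difference is that the confidence interval discloses chance error and does not disclose confounding.

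It is also fair that age adjustment leaves other differences between the cohorts untouched, including the renal exclusion in survivors only.

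**Conclusion.** The concern holds. The late cohort can inform a chronic treatment effect only through a cross-cohort contrast that is implied but not named, and the stated tests leave it open to confounding by age. The bias equals the age slope times the age gap. It is zero if either is zero, and its actual size and sign cannot be determined from the Protocol. On the assumed inputs it is 0.08 to 0.53 SD for realised gaps of 1 to 3 years: smaller than the pilot's 0.79 SD half-width, but invisible in the results.

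This does not invalidate an exploratory pilot. It exposes one of the pilot's intended products, the effect size, to an avoidable error. Confidence is moderate because no ages and no age dependence of ULM are given.

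**What to change.** In Statistics:

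- Name survivors versus Timepoint 1 as an exploratory contrast.
- Estimate it with one linear model of each ULM parameter on cohort and age at scan, on the log scale where skewed, with that choice made per parameter before the cohorts are compared.
- Report the adjusted difference and its 95% CI beside the unadjusted one. Keep a rank-based version as a sensitivity test.
- Tabulate age at scan by cohort.
- State that Timepoint 1 patients have recently diagnosed leukaemia and, since the scan is allowed until before day 50, may already have begun treatment. The adjusted difference is therefore not a pure chronic treatment effect.
- State that the late result applies to survivors without known clinically evident renal impairment.

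No patient, visit or procedure is added: the identification list (Data collection and data storage) already holds date of birth and study date. The cost is precision if age proves irrelevant. The half-width rises from 0.79 SD to 0.80 with no gap, 0.83 at 2 years, 0.85 at 3 years and 0.94 at 5 years. At a correlation of 0.5 it falls instead, to about 0.70–0.74 for gaps up to 3 years. A linear age term may leave a small residual if the relation is curved, and the stated conclusion becomes more modest.

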## **Recruitment**

Patients (and parents) will be informed about the possibility to participate in the study when visiting the pediatric clinic for hematology and oncology (including its outpatient clinics) or attending the follow-up consultation (Department for internal Medicine / Med 5 University Hospital Erlangen). If patients and their parents are interested to participate, they will be fully informed about the aims and methods (especially about the scientific/explorative nature of the study), the benefits and risks, and the revocability of participation in the study before giving their consent prior to study initiation. Patients in childhood and adolescence are additionally informed and educated about the study and its procedure in an age-appropriate manner.

